## 1 INTRODUCTION

This document is a protocol for a clinical research study sponsored by Masimo Corporation. The study will be conducted in compliance with the ethical principles that have their origin in the Declaration of Helsinki. In participating in the study, the Investigator agrees to adhere to all stipulations of this protocol, the conditions of IRB/IEC approval, ISO-14155, and International Conference on Harmonization Good Clinical Practice guidelines ICH GCP.

### 1.1 Background and Rationale

Masimo Corporation is a developer of noninvasive technologies for the measurement and monitoring of physiological variables, such as arterial oxygen saturation ( $SpO_2$ ), total hemoglobin concentration ( $SpHb$ ), carboxyhemoglobin concentration ( $SpCO$ ), methemoglobin concentration ( $SpMet$ ) and acoustic respiration rate monitoring (RRa). These technologies are noninvasive and have a good patient safety record.

Masimo has also developed regional oximetry technology for the detection of deep tissue oxygen saturation. The Masimo O3™ monitoring system consists of a bedside monitor, the O3 regional oximeter module, and near infra-red spectroscopy (NIRS) sensors. NIRS has become an essential tool for monitoring cerebral oxygenation during sedation, operation especially in pediatric patients. Additionally, using NIRS to monitor the difference between somatic and cerebral oxygenation may provide additional physiological information. Published studies (Hoffman et al) have shown that this non-invasive methodology is useful for early and quantitative detection of shock. It has also been shown to be related to the adequacy of mean arterial pressure (MAP), hematocrit, and  $PaCO_2$  during cardiopulmonary bypass (White et al.).

The Masimo O3 Regional Oximeter consists of the following components as a system: O3 Module, O3 Sensor, and Masimo Root (display monitor). The O3 Module receives power from the display monitor. The measurements are generated from the O3 Sensor attached to the patient at proximal end and connected to the O3 Module at the distal end. The measures are taken and displayed on the Masimo Root monitor. The O3 regional oximeter sensors contain a 4-wavelength LED emitter and two light detectors for the detection of deep tissue and superficial oxygenation. The system is designed to allow the near-infrared light to superficially penetrate the scalp, skull and brain tissue. Using multiple wavelengths of light and spatially distributed photo-detectors to interrogate the deep tissue, the O3 system measures regional saturation of oxygen ( $rSO_2$ ) by establishing a relationship between the light absorbed by the tissue and its oxygen saturation. The O3 system has received US FDA 510(k) clearance for adult and pediatric patients.

In addition to the 510(k) cleared adult and pediatric O3 sensors, Masimo has also developed an O3 neonatal sensor for use with the neonatal population. This investigational sensor is similar to the FDA-cleared adult and pediatric sensors in design and intended use, however the sensor footprint has been reduced for these patients.

### 1.2 Study Devices

#### Investigational

- Masimo O3 Neonatal sensors

#### Cleared Devices

- Masimo O3 Regional Oximetry System
- Masimo Radical-7 pulse co-oximeter device
- Masimo RD SET Pulse Oximeters
- Masimo Root patient monitoring and connectivity platform

## 1.3 Risk/Benefits

**Benefits:** There is no benefit to the individual for participation in this research study. No compensation will be paid to the participants or their families. Future benefits might include a reduction in invasive procedures due to the ability to obtain noninvasive blood parameter measurements.

**Risks:** Risks from all Masimo sensors are minimal since the technology uses non-invasive optical sensors.

As with all optical sensors, the investigational device has the risk of thermal burn. The design includes safeguards and this risk is believed to be low. Pressure damage may occur to the tissue if the sensor is placed too tightly. Sensors will be attached with adhesive and may be secured by a supplemental headband. This risk is believed to be low. Optical exposure is minimized by procedure and low power.

All patient-contacting materials including the adhesive used in the design of the regional oximetry sensors are biocompatible, compliant with ISO-10993-5 and ISO-10993-10 testing, and the results demonstrate that the materials are non-toxic, and non-irritating, and non-sensitization. The sensors have been subjected to performance, mechanical, and electrical testing, skin surface temperature and results demonstrate that the sensors meet the requirements for safety and effectiveness for intended use of the product, refer to investigational brochure for further details.

**Patient cable risk:** Entanglement of the sensor cables may occur but the research personnel will be present during the study to avoid such an occurrence.

## 2 STUDY OBJECTIVES

The aim of the study is to compare the performance of the O3 cerebral oximeter and sensor to a 510(k) cleared NIRS device on neonatal subjects based on data collected from the cutaneously placed forehead sensors.

## 3 STUDY DESIGN

This is a prospective, non-randomized, single arm study design to compare the cerebral oxygenation trending data between Masimo's neonatal sensor and a currently cleared NIRS device in the neonatal population using convenience sampling in a clinical environment. This study may be used to support regulatory filings for Masimo O3 system using the neonatal sensor.

## 5 SUBJECT SELECTION AND WITHDRAWAL

### 5.1 Number of Subjects

Subjects will be healthy and non-healthy newborns at Stanford University Medical Center. A convenience sampling with at least 10 subjects and up to 25 subjects with diversified demographics (age, gender, ethnicity, skin tone, comorbidities, etc.) will be recruited and enrolled at this site with the following inclusion and exclusion criteria.

### 5.2 Inclusion Criteria

- Less than 10 kg
- Subjects less than or equal to 28 days old

### 5.3 Exclusion Criteria

- Underdeveloped skin at sites of sensor placement
- Jaundice or hyperbilirubin
- Subject has skin abnormalities affecting the sensor placement area such as psoriasis, eczema, angioma, scar tissue, burn, fungal infection, or substantial skin breakdown that would prevent monitoring of oxygenation levels during the study
- Subject deemed not eligible based on Principal Investigator's judgment

## 5.4 Study Timelines

The anticipated duration of subject participation in this study will not exceed 1 hour during their stay. The sensors may be placed continuously to enable noninvasive data collection. The study enrollment period is expected to be approximately 1 year.

## 5.5 Subject Recruitment and Screening

Potential subjects will be recruited from the patient pool at Stanford University Medical Center. A process for explaining the subject recruitment and screening for the clinical research study will take place during recruitment to determine if an individual is eligible to participate in the study. This will also include a description of the process for obtaining informed consent and HIPAA.

## 5.6 Withdrawal of Subjects

Informed consent discussions will explicitly include emphasis that neither patient enrollment nor patient withdrawal from the study will result in any alterations to the standard clinical care. Participant's parent/legal guardian may elect to withdraw their child at any time without any consequences or loss of benefits to which they are entitled. As the subject, the neonate may be withdrawn from the study prior to expected completion for reasons such as safety concerns, failure to protocol requirements, subject consent withdrawal, etc.

Any data collection until the time of subject's withdrawal may be included in the final data analysis unless the subject withdraws their consent. Information of the subject's withdrawal should be documented in the case report forms (CRFs) and include clear documentation of the reason for withdrawal to the Sponsor.

In case a subject leaves the study prematurely, another subject may be recruited.

## 6 STUDY DEVICE

### 6.1 Description

#### FDA-cleared device:

Masimo O3 regional oximetry uses near-infrared spectroscopy (NIRS) to continuously monitor absolute and trended regional tissue oxygen saturation (rSO2) in the cerebral region. It has received 510(k) clearance marking for use with adult and pediatric patients. The O3 system is comprised of a module, a sensor and a Root monitor. The Radical-7 pulse co-oximeter will be connected to Root patient monitoring platform. All components of the O3 system is cleared except for the sensor. The O3 Neonatal sensor will be considered as an investigational device.

The Root with Radical 7 Pulse CO-Oximeter and accessories are indicated for the continuous non-invasive monitoring of functional oxygen saturation of arterial hemoglobin (SpO2), pulse rate, carboxyhemoglobin saturation (SpCO), methemoglobin saturation (SpMet), total hemoglobin concentration (SpHb), and/or respiratory rate (RRa). The Root is part of the O3 system as it is used to display the readings produced from the sensor.

The Radical 7 pulse CO-oximeter is a noninvasive patient monitor that continuously measures and monitors in real-time the oxygen saturation of arterial hemoglobin (SpO2), and pulse rate (PR), among other parameters, and is for use with adult, pediatric, and neonatal patients during both in motion and no motion conditions, and for patients who are well or poorly perfused in hospitals, hospital-type facilities, mobile, and home environments.

The RD SET™ Series disposable sensors are indicated for the continuous noninvasive monitoring of functional oxygen saturation of arterial hemoglobin (SpO2) and pulse rate (measured by an SpO2 sensor) for use with adult, pediatric, infant, and neonatal patients during both no motion and motion conditions, and for patients who are well or poorly perfused in hospitals, hospital-type facilities, mobile, and home environments.

## Investigational devices:

The investigational O3 Neonatal sensor is similar to the 510(k) cleared O3 Adult and Pediatric sensor in design and functionality. The neonatal sensor's physical design has been modified in dimension and shape to accommodate a better fit in neonatal patients. The neonatal sensor will be equipped with the same or similar technology and materials as the Masimo 510(k) cleared adult and pediatric sensors, and is not anticipated to pose additional risk to human subjects than the 510(k) cleared sensors.

## 6.2 Device Accountability

### 6.2.1 Receipt of Study Device

Upon receipt of the study device supplies, an inventory must be performed and the device accountability log filled out and signed by the person accepting the shipment. It is important that the designated study staff counts and verifies that the shipment contains all the items noted in the shipment inventory. Any damaged or unusable study devices in a given shipment will be documented in the study files. The investigator must notify the study sponsor of any damaged or unusable study devices that were supplied to the investigator's site.

### 6.2.2 Use of Study Device

Use of devices and sensors will be documented on case report forms for each subject.

### 6.2.3 Return or Destruction of Study Device

At the completion of the study, there will be a final reconciliation of study devices and sensors shipped, devices/sensors used, and devices/sensors remaining. This reconciliation will be logged on the device accountability log. Any discrepancies noted will be investigated, resolved, and documented prior to return or destruction of unused study devices. Devices destroyed on site will only be upon written instruction from the sponsor and will be documented in the study files.

### 6.2.4 Device Deficiencies

Device deficiencies are defined as the inadequacy of a medical device with respect to its identity, quality, durability, reliability, safety or performance. Record all device deficiencies on the case report form and report to the Sponsor.

## 7 STUDY PROCEDURES

### 7.1 Informed Consent and Screening Procedure

- 7.1.1 Following identification of a potential eligible subject as defined by the inclusion and exclusion criteria, the child's parent(s), guardians(s), legally authorized representative, will be approached by the study staff. The study research staff will explain the purpose and procedures of the study in respect to potential risks & benefits, and clarification of subject's rights & privacy and allow ample amount of time for participating in the described study. The research team will emphasize that participation is voluntary, has no monetary compensation, and declining the participation will not affect their child's medical care.
- 7.1.2 As a subject, the neonate must meet all the inclusion criteria and none of the exclusion criteria prior to being enrolled in the study.
- 7.1.3 This protocol requires written informed consent in accordance with applicable federal and state regulations, as well as institutional review board (IRB). If the child's parent(s)/legal guardian(s) express interest in participating in the study, they will be asked to read the written informed consent.
- 7.1.4 Once the parent(s)/legal guardian(s) questions have been answered and the informed consent signed and dated, the

Principal Investigator or delegate will also sign the informed consent document, approving that the subject will be enrolled in the study. The Investigator shall retain the original copy of the signed informed consent document in each subject's records and provide a copy to the subject. The investigator shall not enroll any subject to participate in the study or consent any subject prior to receiving IRB approval of the informed consent form.

7.1.5 Subject's demographic information which may include, but is not limited to: gender, age, weight, height, race, ethnicity, [REDACTED]

[REDACTED] will be recorded on the case report form (CRF).

## 7.2 Noninvasive Readings

7.2.1 Demographic information and medical history will be obtained for each enrolled subject prior to the start of the procedure.

7.2.2 One Masimo O3™ cerebral oximetry sensor and one 510(k) cleared sensor will be placed [REDACTED]

[REDACTED]  
7.2.3 If there is no standard-of-care pulse oximetry sensor attached to the subject, a Masimo pulse oximetry sensor will be placed on to the subject. (If there is a standard of care sensor present, record the SpO2 reading from the standard-of-care sensor on the CRF prior to beginning data collection with any regional oximetry sensor. The Masimo sensor will not be used to make any clinical decisions and is only meant for data collection purposes.)

7.2.4 [REDACTED]

[REDACTED] Masimo's regional oximeter module will be connected to Root for regional oximetry data collection.

7.2.5 Masimo regional oximetry sensor will be connected to the O3 module (POD). [REDACTED]

[REDACTED] Record the start time on the CRF and begin data collection [REDACTED]

7.2.6 Collect data for at least five minutes. [REDACTED]

[REDACTED]

7.2.7 [REDACTED]

[REDACTED].

7.2.8 [REDACTED]

[REDACTED]  
[REDACTED]  
[REDACTED]  
[REDACTED]

## 8 STATISTICAL ANALYSIS

### 8.1 Sample Size Determination

This study will use a convenience sampling of at least 10 subjects, but up to 25 subjects may be enrolled to account for possible events such as subject withdrawal, device deficiencies, and/or incomplete cases.

### 8.2 Data Analysis

There are no acceptance criteria for this study. Bias, Precision and RMS values will be calculated and reported between the two test devices but there are no invasive reference for actual accuracy measurements. Performance metrics are not required as this is a convenience sample study.

## 9 SAFETY AND ADVERSE EVENTS

### 9.1 Definitions

The definitions for adverse event, adverse device effect, serious adverse event, serious adverse device effect, and unanticipated adverse device effect are provided below (ISO 14155:2011, 21 CFR 812.3(s)).

- Adverse Event (AE): an adverse event is any untoward medical occurrence in a subject which need not be related to the device under investigation.
- Adverse Device Effect (ADE): an adverse device effect is any untoward or unintended response to a medical device which may result from insufficiencies in the instructions for use or deployment of the device, or from use error.
- Serious Adverse Event (SAE): a serious adverse event is an adverse event that results in death, inpatient hospitalization, severe or permanent disability, a life threatening illness or injury, fetal distress, fetal death, a congenital abnormality, a birth defect, or medical or surgical intervention to prevent permanent impairment to body or structure.
- Serious Adverse Device Effect (SADE): a serious adverse device effect is an adverse device effect that results in death, inpatient hospitalization, severe or permanent disability or is life threatening.
- Unanticipated Adverse Device Effect (UADE): any serious adverse effect on health or safety or any life threatening problem or death caused by or associated with, a device, if the effect, problem, or death was not previously identified in nature, severity or degree of incidence in the investigational plan, or application (including a supplementary plan or application) or any other unanticipated serious problem associated with a device that related to the rights, safety or welfare of subjects.

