### 9.2 Anticipated Adverse Events:

Sensor may cause slight and temporary redness, skin discomfort or irritation, which should fade away shortly after sensor removal.

Sensor may cause thermal burn; however, the design includes safeguards and this risk is believed to be minimal.

Sensor may cause an allergic reaction to the adhesive or other materials used in the sensors; however, all patient contacting materials have undergone biocompatibility testing and conforms to all relevant standards.

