## 11 MONITORING PLAN

11.1 As the sponsor of this clinical investigation, Masimo Corporation is required by 21 CFR, Part 812, of the Food and Drug Administration regulations to monitor and oversee the progress of the investigation. The monitor(s) assigned by Masimo Corporation to this task will be a direct employee from the Clinical Research department trained on departmental SOPs on conduct and monitoring of sponsored studies.

11.2 In accordance with good clinical practices guidelines, there will be at least three scheduled monitoring visits to ensure overall regulatory compliance of the study:

[REDACTED]

[REDACTED]

[REDACTED]

[REDACTED]

11.3 The monitor will contact and visit the investigator and will be allowed, on request, to have access to all source documents needed to verify the entries in the CRFs and other GCP-related documents (IRB approvals, IRB correspondences, and ICFs) provided that subject confidentiality is maintained in agreement with HIPAA regulations.

11.4 It will be the monitor's responsibility to inspect the CRFs at regular intervals throughout the study, to verify the adherence to the CIP and the completeness, consistency and accuracy of the data being entered on them.

11.5 During each visit, the monitor will also verify presence of informed consent, adherence to the inclusion/exclusion criteria, and documentation of SAEs/SADEs and protocol deviations/violations, and check CRF against source documentation.

11.6 After each visit, the monitor will provide a follow up letter to the investigator within 4 weeks of visit completion. The follow up letter will detail findings and open action items observed during the visit. It is the responsibility of the Principal Investigator and Study Coordinator(s) to respond to the findings of the follow up letter, and complete any open action items as soon as possible but no later than 60 days of receiving the follow up letter. Any open action items not completed within the time allowed may be sufficient grounds for study site suspension or termination; it will be up to the sponsor to determine whether any incomplete action items are sufficient grounds for suspension or termination. See Section 16 for details on suspension and termination.

11.7 Depending on the quality of the data and/or changes to factors affecting patient safety, additional monitoring visits may be necessary according to the sponsor's discretion.

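### In section 9.1 the SADE definition omits the intervention outcome that makes an event an SAE, and the ADE sentence can be read to leave out harm from a correctly applied sensor

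*Combined protocol and SAP*

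**What the plan says.** All the definitions are in section 9.1.

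- **ADE.** The sentence opens broadly: "an adverse device effect is any untoward or unintended response to a medical device". It continues with "which may result from insufficiencies in the instructions for use or deployment of the device, or from use error". It does not name malfunction or the normal operation of a correctly applied sensor, and it has no wording to mark the named causes as examples.
- **SADE.** "a serious adverse device effect is an adverse device effect that results in death, inpatient hospitalization, severe or permanent disability or is life threatening".
- **SAE.** This definition has the same four outcomes and five more: "fetal distress, fetal death, a congenital abnormality, a birth defect" and "medical or surgical intervention to prevent permanent impairment to body or structure".
- **UADE.** This covers a serious effect "caused by or associated with, a device", provided it was not already identified in nature, severity or degree of incidence.

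Section 1.3 gives thermal burn as a risk of the investigational device. Section 9.2 lists it again: "Sensor may cause thermal burn; however, the design includes safeguards and this risk is believed to be minimal". Section 9.2 also lists allergic reaction to the adhesive or other sensor materials. Neither section ties these two risks to misuse. Pressure damage, by contrast, is linked in section 1.3 to a sensor applied too tightly.

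The terms are used later in the protocol. Under section 11.5 the monitor verifies "documentation of SAEs/SADEs and protocol deviations/violations". Under section 14 the investigator evaluates adverse events and adverse device effects when judging whether the study may safely continue.

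**The concern.** The neonatal sensor is the only investigational component (section 6.1), and section 3 says the study may support regulatory filings. The ADE and SADE classes are where the protocol separates harm due to a device from other harm. Two features of section 9.1 work against that.

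First, the outcomes that make an event serious differ according to whether the event is called an adverse event or a device effect, and no reason is given. The outcome left out is a plausible route to seriousness for a sensor injury: treatment given to avert lasting damage.

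Second, the ADE sentence fits risks of application, such as over-tight placement. It fits less clearly the risks that the protocol attributes to the sensor itself. Whether a burn under a correctly placed sensor is an ADE would depend on how the site reads one clause.

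What is at stake is the classification of serious device effects. With 10 to 25 infants (section 8.1), a single event could decide whether any SADE is recorded.

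**Working it through.** The plan gives no figure to reproduce. The check compares the definitions and follows one hypothetical event through them.

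**Step 1: compare the outcome lists in section 9.1.**

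| Outcome | SAE | SADE |
|---|---|---|
| Death | yes | yes |
| Hospital admission | yes | yes |
| Severe or permanent disability | yes | yes |
| Threat to life | yes | yes |
| Fetal distress | yes | no |
| Fetal death | yes | no |
| Congenital abnormality | yes | no |
| Birth defect | yes | no |
| Intervention to avert permanent impairment | yes | no |

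SAE has 9 outcomes and SADE has 4, so 9 − 4 = 5 are absent from SADE. Four of those five are fetal or congenital and cannot result from a forehead sensor on an infant already born. That leaves 5 − 4 = 1 relevant omission. Of the 9 − 4 = 5 SAE outcomes that could apply here, SADE carries 4.

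**Step 2: classify one event.** Suppose that a correctly applied sensor causes a burn, that the burn is treated surgically to avert permanent damage, and that no other seriousness outcome is met.

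| Class | Causal clause read as illustrative | Causal clause read as restrictive |
|---|---|---|
| AE | yes | yes |
| SAE | yes | yes |
| ADE | yes | no |
| SADE | no | no |
| UADE | depends on severity | depends on severity |

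The SADE row is no in both columns, for different reasons. On the illustrative reading the event is an ADE but the outcome list excludes it. On the restrictive reading it is not an ADE at all. The outcome-list gap therefore does not depend on how the ADE sentence is read.

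The UADE row is open. That definition has its own causal wording and does not pass through the ADE definition. Section 9.2 anticipates thermal burn but states no severity, so a burn needing surgery could count as not previously identified in severity.

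**Step 3: follow the consequences.**

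- Section 9.3: every adverse event goes on the CRF and the adverse event form and is reported to the sponsor. SAEs and UADEs go within 48 hours, other events within 5 business days. SAEs also go to the IRB. No rule there depends on ADE or SADE class.
- Section 11.5: the monitor checks SAEs as well as SADEs, so the burn is checked as an SAE.
- Section 14: the investigator evaluates all adverse events, so the burn is evaluated as an AE.
- Section 13.4: termination for safety turns on a UADE, not on an ADE or SADE.
- Section 6.2.4: a safety inadequacy of the device is also recorded as a device deficiency. That entry describes the device and does not class the subject's event as an ADE or SADE.

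The event reaches the CRF, the sponsor and the IRB. Its SADE label is lost and, on one reading, its ADE label too.

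**The case against.** The strongest reply has four parts.

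1. The ADE sentence begins with any untoward response and then uses permissive wording about cause, so a burn caused by the sensor fits the opening words. This stands. It cannot be said flatly that such a burn is not an ADE. What remains is that the sentence allows both readings. Sections 1.3 and 9.2 do not say that burns arise only under a correctly applied sensor, but they do not tie them to misuse either.
2. A reader might infer that serious device harm could go unreported. The documents do not support that: section 9.3 captures every adverse event whatever its device class, and reports of SAEs to the IRB may include the relationship to the device. A reader might also infer that a burn escapes UADE because section 9.2 anticipates it. That ignores the severity limb of the UADE definition.
3. A reader might infer that a regulatory filing would show no serious device harm after a sensor injury. The plan specifies no ADE or SADE tabulation. Section 8.2 plans only bias, precision and RMS, and section 3 says only that the study may support filings. An effect on a filing is conjecture.
4. The count of 4 against 9 outcomes makes the gap look larger than it is, because only one missing outcome applies to these infants. This also stands.

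None of this answers the outcome-list gap. On either reading of the ADE sentence, the same outcome is serious for an adverse event and not for a device effect.

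**Conclusion.** The point holds, as a minor one. The firm part is the SADE list: it omits one relevant SAE outcome, so a device-caused injury that is serious only on that ground is an SAE but not an SADE. The less firm part is the ADE sentence, which is ambiguous. Only its restrictive reading excludes a burn or adhesive reaction from a correctly applied sensor.

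The effect is limited to misclassifying serious device effects in a study of 10 to 25 infants, each taking part for no more than 1 hour (section 5.4). No reporting deadline, endpoint or termination rule depends on the affected labels. The conclusion assumes that the injury meets none of the four outcomes the lists share. If it met one of them and was accepted as an ADE, it would be an SADE under the present wording.

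**What to change.** Make two changes in section 9.1.

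- Define an SADE as an ADE that meets any outcome in the SAE definition, so that the two lists cannot diverge.
- Define an ADE as any adverse event related to use of a study device, including malfunction, normal operation, insufficient instructions or deployment, and use error. This brings it into line with the risks named in sections 1.3 and 9.2.

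The adverse event form should follow the same wording.

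The cost is two reworded definitions and an aligned form, made by amendment under section 13.2. Study procedures, sample size and analysis do not change. The ADE and SADE counts may be slightly higher than under the present wording.

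### The serious adverse event definition omits prolongation of an existing hospital stay, although the subjects are newborns studied while in hospital

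*Combined protocol and SAP*

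**What the plan says.** Section 9.1 states that "a serious adverse event is an adverse event that results in death, inpatient hospitalization, severe or permanent disability". It then adds life-threatening illness or injury and several fetal and congenital outcomes, and closes with "or medical or surgical intervention to prevent permanent impairment to body or structure". The list has no open-ended item, and a longer stay is not on it. The device counterpart (SADE) is shorter: "a serious adverse device effect is an adverse device effect that results in death, inpatient hospitalization, severe or permanent disability or is life threatening".

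Relation to the device is not needed for an event to count: "an adverse event is any untoward medical occurrence in a subject which need not be related to the device under investigation". A UADE must be serious and device-associated, and must be an effect that "was not previously identified in nature, severity or degree of incidence in the investigational plan" (or in an application), or else fall under a closing limb, "or any other unanticipated serious problem associated with a device that related to the rights, safety or welfare of subjects".

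Section 9.3 has two tiers. SAEs and UADEs must reach the sponsor within 48 hours, and both are also reported to the IRB. All other adverse events should reach the sponsor within 5 business days, with no IRB report mentioned. Every adverse event, whatever its tier, is to be recorded and promptly reported to the sponsor.

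Sections 5.1 and 5.4 describe the subjects: healthy and non-healthy newborns at one medical center, taking part for no more than 1 hour during their stay.

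**The concern.** A hospitalization criterion separates serious from non-serious events well when subjects start outside hospital. Here they start inside it. An event in a baby who is already a patient will not ordinarily result in an admission. The realistic hospitalization outcome is a later discharge, and the definition does not mention that.

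The label matters because Section 9.3 uses it to set both the outer time limit to the sponsor and the route to the IRB. If a longer stay is an event's only serious consequence, the printed rules put it in the slower tier and name no IRB report. The plan itself treats the subjects as a vulnerable population (Section 12), so the definition should fit their circumstances.

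**Working it through.** The plan gives no figure to reproduce. The check is to take one event through the printed rules: an adverse event in a newborn already in hospital, whose only serious consequence is a longer stay.

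1. **Is it an adverse event?** Yes, whether or not the device caused it (9.1).
2. **Is it an SAE?** By construction there is no death, disability, threat to life, fetal or congenital outcome, or intervention to prevent permanent impairment. The only criterion left is inpatient hospitalization. The baby is already admitted, so the event does not result in admission. As printed, it is not an SAE.
3. **Is it a UADE?** This depends on its relation to the device.
   - *Unrelated to the device:* no, because both limbs of the definition require an association with a device.
   - *Device-associated and not previously identified:* it can be, if judged serious. The UADE definition does not tie that word to the SAE list.
   - *Device-associated and anticipated in 9.2:* uncertain. Section 9.2 describes skin redness and irritation as slight and short-lived. On burns it says "Sensor may cause thermal burn; however, the design includes safeguards and this risk is believed to be minimal", which gives a likelihood but no severity. Allergic reaction also has no severity stated. An effect bad enough to delay discharge may therefore exceed what was identified, and the UADE route would open.
4. **What does 9.3 then require?**

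| Event whose only serious consequence is a longer stay | SAE as printed | UADE | Limit to sponsor | IRB report named in 9.3 |
|---|---|---|---|---|
| Unrelated to the device | No | No | 5 business days | None |
| Anticipated device effect | No | Uncertain | 48 hours if UADE, otherwise 5 business days | Only if UADE |
| Device effect not previously identified | No | Yes, if judged serious | 48 hours | Yes |

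**Size of the difference in limits.** Five full days with no weekend between are 5 × 24 = 120 hours, and 120 − 48 = 72 hours. This compares nominal limits only. Section 9.3 does not say when either clock starts, so no actual delay follows from it.

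**Where the omission has effect.** Inpatient hospitalization is mentioned three times: in the SAE definition, the SADE definition and the report content in 9.3. None of the three adds prolongation, but only the SAE definition changes how an event is handled. Section 9.3 sets no rule for SADEs as such, and its report content is expressly not an exhaustive list.

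**Exposure.** With 10 to 25 subjects (8.1) and at most 1 hour each (5.4), the ceiling is 25 × 1 = 25 subject-hours. The documents give no rate for stay-lengthening events, so no expected count can be derived.

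**The case against.** The strongest reply is that the printed list is not the only rule. The lead-in to 9.1 cites ISO 14155:2011, and Section 1 separately binds the investigator to ISO-14155, ICH GCP and the conditions of IRB approval. Section 12.3 also gives the IRB responsibility for continuing review. This stands in part. Those texts and conditions are not supplied, so they may require faster or wider reporting. They do not alter the printed list, however, and the lead-in presents that list as the definitions in use. The statement about the IRB must therefore be limited to what 9.3 names.

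A second reply is that the events most securely outside the faster tier are those unrelated to the device, often from underlying illness, and that reporting them sooner protects nobody. There is force in this, since participation is brief and the sensor is noninvasive. But the plan already gives unrelated events SAE status when they meet another criterion, so relatedness does not explain leaving out a longer stay.

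A reader might infer that anticipated device effects, such as a burn that delays discharge, are plainly excluded from 48-hour and IRB reporting. The documents do not support that, because 9.2 sets no severity for burns or allergic reactions and the UADE route may apply. A reader might also infer that serious events would be lost. They would not: every adverse event is recorded and promptly reported to the sponsor (9.3), and Section 14 has the Principal Investigator evaluate each one and decide whether the study is safe to continue.

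**Conclusion.** The point holds in a narrow form. As printed, the SAE definition does not cover a lengthened stay in subjects who are already in hospital. For events unrelated to the device, the consequence is clear: a nominal limit of 5 business days instead of 48 hours, and no IRB report named in 9.3. For anticipated device effects the classification is uncertain.

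The practical effect is small. It concerns timing and routing only, in a study with at most 25 subject-hours of participation, and the device comparison in 8.2 does not depend on it. The conclusion assumes that the site applies 9.1 and 9.3 literally and that neither the IRB's conditions nor the cited standards impose something stricter. The visible text gives no follow-up window for adverse events, and parts of 7.2.6 to 7.2.8 are redacted. Whether a later discharge would be noticed therefore cannot be judged, and this is not counted against the plan. It is a cheap improvement, not a defect that threatens the study.

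**What to change.** In the SAE definition in 9.1, replace inpatient hospitalization with *inpatient hospitalization or prolongation of existing hospitalization*. That change alone moves the affected events into the 48-hour tier and the stated IRB report.

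Matching edits to the SADE definition and to the report content in 9.3 are optional. They make the labels consistent and have no effect on reporting times. If the Adverse Event Report Form (not supplied) repeats the list, it should be updated too.

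The cost is one amendment, signed by the Principal Investigator and the sponsor and approved by the IRB (13.2), with no added study procedures. The downside is possibly a few extra 48-hour and IRB reports. Some would be for stays lengthened by underlying illness, because non-healthy newborns are eligible and SAE status does not depend on relation to the device.
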